10.7 Comprehensive AEs and Potential Risks

The descriptions and grading scales found in the current version of the NCI CTCAE (v.4) will be utilized for AE reporting. A copy of the current CTCAE can be downloaded from the CTEP web site: <http://ctep.cancer.gov/reporting/ctc.html>. AEs will be collected according to the study calendar schedule in **Section 6.4**.

10.7.1 Eribulin

The most common AEs reported in >1 of 10 subjects receiving eribulin are shown below based on 827 breast cancer subjects who received the recommended dose in Phase II and Phase III breast cancer studies.

AE	Adverse Reactions (all grades)
Blood and Lymphatic System Disorders	
Neutropenia	54.5%
Leucopenia	22.1%
Anemia	20.3%
Nervous system disorders	
Peripheral neuropathy	32%
Headache	11%
Asthenia/Fatigue	52.8%
Mucosal inflammation	9.8%
Pyrexia	16.6%
Gastrointestinal disorders	
Constipation	16.3%
Diarrhea	15.0%
Nausea	35.1%
Vomiting	14.5%
Musculoskeletal and connective tissue disorders	
Arthralgia/Myalgia	12.7%
Back pain	1.9%
Bone pain	1.7%
Pain in extremity	4.7%
Investigations	
Weight decreased	9.7%
Metabolism and nutrition disorders	
Decreased Appetite	18.5%
Respiratory, thoracic, and mediastinal disorders	
Cough	4.7%
Dyspnea	5.6%
Skin and subcutaneous tissue disorders	
Alopecia	49.7%
Infections and Infestations	
Urinary Tract Infection	4.8%

10.7.2 Everolimus

Adverse reactions reported in at least one phase III trial in at least 5% of patients and at a higher rate in the everolimus arm than in the placebo arm are shown below.

System Organ Class	Very common	Common
Infections and infestations	Infections ¹	-
Metabolism and nutrition Disorders	decreased appetite ²	diabetes mellitus
Vascular disorders		hypertension

Nervous system disorders	dysgeusia, headache	-
Respiratory, thoracic and mediastinal disorders	cough, pneumonitis ³ epistaxis, dyspnea	--
Gastrointestinal disorders	stomatitis ⁴ , diarrhea, nausea, vomiting	dry mouth
Skin and subcutaneous tissue Disorders	rash, dry skin, pruritus nail disorder	Acne
General disorders and administration site conditions	fatigue, asthenia, mucosal inflammation, edema peripheral, pyrexia	-
Investigations	weight decreased	-

¹ Includes all those reported for the system organ class and isolated cases of opportunistic infections, including reactivation of hepatitis B (<1%); ² Reported as anorexia in C2240 according to MedDRA v11.0;

³ Includes alveolitis, interstitial lung disease, lung infiltration, pneumonitis, pulmonary alveolar hemorrhage, and pulmonary toxicity; ⁴ Includes aphthous stomatitis and mouth and tongue ulceration

Other notable adverse reactions, occurring in at least one pivotal trial more frequently with everolimus than with placebo, but with an incidence of <5% are listed below. All terms included are based on the highest percentage reported in a pivotal trial.

- *Blood and lymphatic system disorders*: Uncommon: Pure red cell aplasia (<1%).
- *Metabolism and nutrition disorders*: Common: dehydration (2.5%), exacerbation of pre-existing diabetes mellitus (1.1%). Uncommon: new onset of diabetes (<1%).
- *Psychiatric disorders*: Common: insomnia (3.3%).
- *Nervous system disorders*: Uncommon: ageusia (<1%)
- *Vascular disorders*: Common: hemorrhage (4.7%, various locations); Uncommon: deep vein thrombosis (<1%).
- *Cardiac disorders*: Uncommon: congestive cardiac failure (<1%).
- *Respiratory, thoracic and mediastinal disorders*: Common: pulmonary embolism (1.5%), hemoptysis (1.1%); Uncommon: acute respiratory distress syndrome (<1%).
- *Gastrointestinal disorders*: Common: oral pain (3.7%), abdominal pain (3.6%), dyspepsia (2.9%), dysphagia (2.6%).
- *Skin and subcutaneous tissue disorders*: Common: hand-foot syndrome (4.7%), erythema (3.7%).
- *Musculoskeletal and connective tissue disorders*: Common: arthralgia (2.8%).
- *Renal and urinary disorders*: Common: proteinuria (2.5%), renal failure (2.3%, including acute renal failure), increased day-time urination (1.8%).
- *General disorders and administration site conditions*: Common: chest pain (1.1%); Uncommon: impaired wound healing (<1%).

In all phase III trials, the majority of observed key laboratory abnormalities were reported with an incidence of $\geq 10\%$ (listed in decreasing frequency):

- Decreased hematologic parameters include hemoglobin, lymphocytes, platelets, and neutrophils (or collectively as pancytopenia).
- Increased clinical chemistry parameters include cholesterol, triglycerides, glucose, aspartate transaminases, creatinine, alanine transaminases, and bilirubin.
- Decreased clinical chemistry parameters include phosphate and potassium.

Most of observed abnormalities were mild (Grade 1) or moderate (Grade 2). Grade 4 abnormalities include reductions in lymphocytes (2.2%), hemoglobin (2%), and potassium (2%), neutrophils, platelets, and phosphate (each <1%) and increases in creatinine (1%), cholesterol, AST, ALT, bilirubin, and glucose (each <1%).

10.8 Other AE Factors to Consider

Factors to be considered in assessing the relationship of the AE to study drugs include:

- *The Temporal Sequence from Drug Administration:* The event should occur after the drug is given. The length of time from drug exposure to event should be evaluated in the clinical context of the event.
- *Recovery on Discontinuation (de-challenge), Recurrence on Reintroduction (re-challenge):* Subject's response after drug discontinuation (de-challenge) or subjects response after drug re-introduction (re-challenge) should be considered in the view of the usual clinical course of the event in question.
- *Underlying, Concomitant, Current Diseases:* Each report should be evaluated in the context of the natural history and course of the disease being treated and any other disease the subject may have.
- *Concomitant Medication or Treatment:* The other drugs the subject is taking or the treatment the subject receives should be examined to determine whether any of them may be suspected to cause the event in question.
- *The Pharmacology and Pharmacokinetics of the Test Drug:* The pharmacokinetic properties (absorption, distribution, metabolism and excretion) of the test drug(s), coupled with the individual subject's pharmacodynamics should be considered.

11.0 Statistical Considerations

Primary Objective for Phase I Study

The primary objective of the Phase I portion of the study is to determine the safety and tolerability of everolimus and eribulin, and determine the recommended Phase II dose (RP2D) of the drug combination in patients with resistant metastatic TNBC.

Primary Objective for Phase Ib Study

The primary objective of the Phase Ib portion of the study is to evaluate the event-free survival (EFS) rate for patients with resistant metastatic TNBC at the RP2D of everolimus and eribulin to determine if the drug combination is worthy of further study.

Secondary Objectives for Phase Ib Study

The secondary objectives of the Phase Ib portion of the study are to determine response rate, OS, toxicity, and pharmacokinetics (PK) for everolimus and eribulin in patients with resistant metastatic TNBC.

A further secondary objective is to collect blood, skin punch biopsies, and tumor biopsies before and after treatment from all patients, and perform proteomic analysis to determine the level of inhibition of the PI3K pathway in tumor cells versus non-therapeutic targets.

11.1 Design

11.1.1 Phase I portion

The Phase I portion of this study will use the toxicity equivalence range (TEQR) design of Blanchard and Longmate [35] to evaluate select dose levels of the everolimus in combination with eribulin and to determine the RP2D. In this implementation of the TEQR design, we define the target equivalence range of the DLT rate as 0.20-0.35. DLT rate levels of 0.51 or higher will be considered too toxic and doses that achieve that level will not be revisited. The dose escalation de-escalation rules will be the following. If the rate of participants that experience a DLT is below 0.20 we will escalate, if the rate is above 0.35 we will de-escalate and if it is between 0.20-0.35 we will stay at the current dose. Participants will enter the protocol in cohorts of 3. The starting dose will be dose level 1. This study will end when 12 research participants are studied at a single dose level with a toxicity level below 0.51. Further we also implement the additional rules: 1) terminate the trial if dose level 1 is too toxic, and 2) if the current dose is safe but based on the data the next dose is deemed too toxic, stay at the current dose. The RP2D will be the dose closest to target of 0.25 below 0.51 based on isotonic regression. The dose schedule is provided in Table 11.1 below.

The PMT team for protocol 14036 reviewed the data: dose level 2 was closed after 2 of 3 evaluable participants experienced DLTs an observed rate of 67%; dose level 1, we saw 4 DLTs in 8 evaluable participants giving an observed DLT rate of 50% on this dose. Our equivalence range for DLT rate for this trial is 20-35%, our observed rate of 50% is above 35% so we plan to de-escalate. Two participants experienced grade 4 neutrophil count decrease and 2 experienced mucositis (1 grade 3 DLT, 1 participant received 71% of Everolimus due to grade 2 which is a DLT). Thus, the team decided to amend the protocol to allow for two new dose levels at a lower dose of Eribulin, and start the next cohort of patients at dose level B1.

Table 11.1 Dosing Schedule: cycle length is 21 days

Dose level A	Everolimus (oral)	Eribulin (intravenous)
A-1	2.5mg daily (day 1 to 21)	1.4mg/m ² on days 1, 8
A1	5mg daily (day 1 to 21)	1.4mg/m ² on days 1,8
A2	7.5mg daily (day 1 to 21)	1.4mg/m ² on days 1,8
A3	10mg daily (day 1 to 21)	1.4mg/m ² on days 1, 8

Dose level B	Everolimus (oral)	Eribulin (intravenous)
B1	5mg daily (day 1 to 21)	1.1mg/m ² on days 1,8
B-1	2.5mg daily (day 1 to 21)	1.1mg/m ² on days 1,8

Table 11.2 is a pictorial representation of the dose escalation/de-escalation guidelines for a target toxicity of 25% and $\varepsilon_1=5\%$ $\varepsilon_2=10\%$ giving an equivalence range of 20%-35%. The numbers of research participants treated at the current dose is provided in the columns and the number of research participants experiencing a DLT in the rows. Note that this design is similar to a 3+3 design for the first 3 patients seen at a dose as it escalates if 0 study participants experience DLTs, holds if 1 experiences a DLT (33%), and de-escalates if 2 experience a DLT, differing from a 3+3 at sample sizes of 6 and above patients as it holds at 33% toxicity and de-escalates at 36% toxicity or above.

Based on the results of 1,000 simulated trials considering 4 toxicity probability schedules (**Table 11.3**) for the 4 doses in combination with the trial specifications listed above, the median sample size was 18 with 95% confidence limits of 12 and 24 and the sample size

Table 11.2: Dose escalation/de-escalation guidelines (E= escalate, D=de-escalate, S=stay, DU=de-escalate and do not return to this dose).											
		Number of research participants treated on the current dose level (Standard sample size based on a cohort size =3 are bolded.)									
		3	4	5	6	7	8	9	10	11	12
Number of Research Participants Experiencing a DLT	0	E	E	E	E	E	E	E	E	E	E
	1	S	S	S	E	E	E	E	E	E	E
	2	DU	D	D	S	S	S	S	S	E	E
	3	DU	DU	DU	D	D	D	S	S	S	S
	4				DU	DU	D	D	D	D	S
	5						DU	DU	D	D	D
IRB Protocol No. 14036 2/1/2017	6							Version Date: DU	DU		D
Version: 13	7							Page 53 of 79			DU

at the MTD was ≥ 12 in at least 91% of trials. Note **Table 11.3** provides the rates at which each dose level for each schedule was chosen as the MTD (MTD rate) and the average number of research participants seen at each dose (Ave # Pts.).

Table 11.3: Associated rates each dose level is identified as the MTD and average number of patients studied for 4 dose toxicity probability scenarios						
Toxicity Probability Scenarios	Dose levels					No MTD
	-1	1	2	3		
Scenario 1	0.05	0.1	0.25	0.50		
RP2D rate	0.03	0.29	0.56	0.12		0
Ave # Pts.	0.4	5.9	8.1	3.6		
Scenario 2	0.025	0.05	0.20	0.40		
RP2D rate	0.01	0.15	0.58	0.27		0
Ave # Pts	0.08	4.7	8.2	5.8		
Scenario 3	0.025	0.05	0.1	0.25		
RP2D rate	0.01	0.05	0.27	0.66		0
Ave # Pts	0.12	3.8	5.6	9.1		
Scenario 4	0.1	0.25	0.4	0.5		
RP2D rate	0.19	0.55	0.22	0.04		.01
Ave # Pts	2.5	8.27	4.7	1.3		

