4.1 Phase I Study

The Phase I portion of the trial will use the toxicity equivalence range (TEQR) design. Based on this design, the target equivalence range of dose-limiting toxicities (DLTs) is 0.20-0.35. Toxicity levels of ≥ 0.51 will be considered too toxic, and doses which achieve this level will be stopped. Patients will enter the protocol in cohorts of three. This phase will be considered complete when 12 patients are studied at a single dose level with a toxicity level < 0.51 . The RP2D will be the dose closest to the target of 0.25 below 0.51 based on isotonic regression. Based on these requirements, the TEQR design will use a minimum of 6 patients and a maximum of 24 patients (median of 18) to determine the MTD. (see **Section 11**).

The PMT team for protocol 14036 reviewed the data: dose level 2 was closed after 2 of 3 evaluable participants experienced DLTs an observed rate of 67%; dose level 1, we saw 4 DLTs in 8 evaluable participants giving an observed DLT rate of 50% on this dose. Our equivalence range for DLT rate for this trial is 20-35%, our observed rate of 50% is above 35% so we plan to de-escalate. Two participants experienced grade 4 neutrophil count decrease and 2 experienced mucositis (1 grade 3 DLT, 1 participant received 71% of Everolimus due to grade 2 which is a DLT). Thus, the team decided to amend the protocol to allow for two new dose levels at a lower dose of Eribulin, and start the next cohort of patients at dose level B1.

Dosing Schedule: cycle length is 21 days

Dose level A	Everolimus (oral)	Eribulin (intravenous)
A-1	2.5mg daily (day 1 to 21)	1.4mg/m ² on days 1, 8
A1	5mg daily (day 1 to 21)	1.4mg/m ² on days 1,8
A2	7.5mg daily (day 1 to 21)	1.4mg/m ² on days 1,8
A3	10mg daily (day 1 to 21)	1.4mg/m ² on days 1, 8

Dose level B	Everolimus (oral)	Eribulin (intravenous)
B1	5mg daily (day 1 to 21)	1.1mg/m ² on days 1,8
B-1	2.5mg daily (day 1 to 21)	1.1mg/m ² on days 1,8

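### The Phase I termination rule names the starting dose, but the protocol's stated minimum and simulation results fit a rule that applies to the lowest dose

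*Combined protocol and SAP*

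**What the plan says.** Section 11.1.1 sets the DLT equivalence range at 0.20-0.35 and treats an observed rate of 0.51 or more as too toxic. On the start it says: "The starting dose will be dose level 1". Table 11.1 puts a lower level under it in each schedule: A-1 below A1, and B-1 below B1. Two additional rules follow, the first being to "terminate the trial if dose level 1 is too toxic".

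Table 11.2 codes 2 or 3 DLTs in 3 patients as DU, defined as "DU=de-escalate and do not return to this dose". The text beside it says that the design holds at 1 DLT in 3 "and de-escalates if 2 experience a DLT".

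The simulation results are attributed to "the trial specifications listed above, the median sample size was 18 with 95% confidence limits of 12 and 24". Table 11.3 ("Associated rates each dose level is identified as the MTD and average number of patients studied") includes level -1 in all four scenarios and has a column for no MTD. Section 4.1 says "the TEQR design will use a minimum of 6 patients and a maximum of 24 patients", and Section 11.2 repeats the minimum of 6.

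The amendment text in Section 11.1.1 reports 4 DLTs in 8 evaluable patients at dose level 1, adds two levels with less eribulin, and decides to "start the next cohort of patients at dose level B1". The termination rule keeps its wording.

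**The concern.** A rule that ends the trial when the starting dose is too toxic makes the level below it almost unreachable. Level -1 could then be reached only when level 1 shows a rate above 0.35 but below 0.51. That does not fit a design whose reported results use level -1 regularly and almost never end without an MTD.

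Two things are at stake. First, the written stopping rule should be the one that produced the stated operating characteristics. Second, a stopping rule should have one meaning when it is needed. Since the amendment, schedule B has its own starting level and its own level below it, and the rule does not mention either. The error leans toward needless termination, not toward extra toxicity.

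**Working it through.** **Inputs.** From Section 11.1.1: cohorts of 3; start at level 1; escalate below 0.20, de-escalate above 0.35, close a level at 0.51 or more; finish at 12 patients on one level with a rate below 0.51; choose the dose by isotonic regression nearest 0.25. From Table 11.3, Scenario 4: true DLT rates 0.10, 0.25, 0.40 and 0.50 at levels -1, 1, 2 and 3.

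**Step 1: the minimum.** If the rule applies to the lowest level, the shortest trial is 3 patients at level 1 (too toxic) plus 3 at level -1 (too toxic), which is 6. This is the stated figure. If it applies to level 1, the shortest trial is 3.

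**Step 2: a floor for no MTD, without simulation.** A first cohort is too toxic when 2 or 3 of 3 patients have a DLT, because 2/3 = 0.67 exceeds 0.51 and 1/3 = 0.33 does not:

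P = 3p²(1-p) + p³

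Scenario 4, p = 0.25: 3(0.0625)(0.75) + 0.0156 = 0.1406 + 0.0156 = 0.156.

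Under the literal rule each of these trials ends with no MTD, so the rate is at least 0.156. The stated rate is .01.

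**Step 3: simulation under both readings.** 20,000 trials per scenario, with the inputs above:

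| Scenario 4 | Stated | Lowest-level rule | Literal rule |
|---|---|---|---|
| No MTD | .01 | 0.008 | 0.182 |
| Level -1 chosen | 0.19 | 0.193 | 0.024 |
| Average patients at -1 | 2.5 | 2.53 | 0.49 |
| Minimum n | 6 | 6 | 3 |

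Repeat runs with other tie handling, or with a cap of 24 patients, move these little. No MTD is 0.007-0.008 (lowest-level) against 0.177-0.182 (literal). Level -1 is chosen in 0.186-0.201 against 0.016-0.030, with about 2.5-2.6 against 0.4-0.5 patients there.

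The average number of patients at level -1 points the same way in the other scenarios:

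| Scenario | Stated | Lowest-level rule | Literal rule |
|---|---|---|---|
| 1 | 0.4 | 0.37 | 0.04 |
| 2 | 0.08 | 0.10 | 0.00 |
| 3 | 0.12 | 0.09 | 0.00 |

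No MTD in Scenario 1 is stated as 0. The lowest-level rule gives 0.000 and the literal rule 0.028.

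**Step 4: could the gap be simulation error?** With the protocol's 1,000 trials, the standard error of a true rate of 0.182 is √(0.182 × 0.818/1000) = 0.012. The gap is 0.182 - 0.01 = 0.172, about 14 standard errors. If the 1,000 trials were split over four scenarios (250 each), the standard error is 0.024 and the gap is still about 7 standard errors.

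**Step 5: schedule A as observed.** A1 had 4/8 = 0.50, below 0.51, so the rule was not triggered.

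**Step 6: schedule B, only if the rule were applied to B1.** The documents give no expected DLT rate for B1, so a range is assumed. With the Step 2 formula, the chance that the first cohort ends the trial with B-1 untried is:

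- p = 0.20: 0.096 + 0.008 = 0.104
- p = 0.30: 0.189 + 0.027 = 0.216
- p = 0.40: 0.288 + 0.064 = 0.352

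**The case against.** Four points can be made for the plan.

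**Table 11.2 does not by itself contradict the rule.** The two rules are introduced as additions to the basic guidelines, and the second one also overrides an E cell. The table is a generic grid for any current dose and has no code for termination, even at the lowest level. This stands, so the DU cell is only supporting evidence. The weight rests on the stated minimum and Table 11.3.

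**The plan does not direct that the trial end at B1.** A reader might infer that it does, but the documents do not support this. The amended text uses dose level 1 for A1 and names B1 separately, so a literal reading does not reach B1. B-1 can be entered only by de-escalating from B1, and Section 11.2 budgets patients for both added doses. Section 10.2 gives the stopping rules to a team that includes the statistician. This also stands. What remains is that no sentence says which rule governs schedule B. If the rule is confined to A1, schedule B has no written termination rule.

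**Schedule A is past the point where the rule could act.** The rule was not met at A1 and the team has moved on. A reader might infer that the move to B1 breached the rule, but 0.50 is below the limit.

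**The simulation does not match every cell.** It puts Scenario 3, level 1 at 0.16 against a stated 0.05, and the Scenario 4 median at 15 against an overall 18. Tie-breaking and selection details that the plan does not give probably explain this. The floor of 0.156 and the minimum of 3 need no simulation, and the level -1 and no-MTD figures barely move across runs. The stated lower limit of 12 is not used here: the plan does not say how it was formed, and the literal rule's limit in Scenarios 2 and 3 varied between runs (12 or 15).

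**Conclusion.** The termination rule is wrong as written. It names the starting dose, while the minimum of 6 and the Scenario 4 results for no MTD and level -1 come from a rule on the lowest dose. The difference is large: no MTD of about 0.18 instead of .01, and level -1 chosen in about 0.02 of trials instead of 0.19. This rests on the design parameters in Section 11.1.1 and on the true rates in Table 11.3. No outside figure is needed.

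A reader might infer that Table 11.3 is in error. On this point it is not: the figures fit the intended rule, and only the sentence needs correcting. Nothing is claimed about the other cells of that table.

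For schedule B the plan is unclear, not shown to be harmful. The probabilities of 0.104 to 0.352 depend on assumed B1 rates and on extending the rule to B1, which no section states.

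**What to change.** In rule 1 of Section 11.1.1, replace dose level 1 with the lowest dose level. Add one sentence: in schedule B the lowest level is B-1, and a too-toxic B1 leads to B-1. No further rule for A-1 is needed, since the documents plan no return to it.

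The cost is a few words and one sentence in an amendment. It needs no patients and no new schedule A simulation, and the stated figures stay as they are.

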11.1.2 Phase Ib portion

In the Phase Ib portion of the trial, a Simon's Optimal two stage design [36] will be used to determine if the combination of everolimus and eribulin results in a greater rate of patients event free at 4 months than eribulin alone. Based on data from the Embrace trial we set the 4 month EFS rate for eribulin to be 45%. We want to determine if the combination has a 4 month EFS rate of 70% or higher, that is to show a 25% improvement. Setting both the type I and type II errors to 0.1 after 12 patients (the number of patients at the RP2D dose at the end of the phase I trial),

- if ≤ 5 patients are event free at 4 months the study will stop.
- If 6 or more patients are event free at 4 months we will add on 15 more patients for a total of 27 at the RP2D.
- If 16 or more patients out of the 27 are event free we will determine the combination worthy of further study.

Primary Endpoints

- Phase I: DLTs as defined in **Section 5.7, Definition of Dose-Limiting Toxicity.**
- Phase Ib: Event free survival (EFS)

Secondary Endpoints Progression Free Survival (PFS)

- Response rate
- Overall survival (OS)
- Toxicity profile
- PK parameters

11.2 Sample Size and Accrual Rate

The expected combined sample size for the Phase I/Ib trial will be 33. We anticipate 18 study participants for Phase I portion, and 15 additional at the RP2D to finish out the Phase Ib portion of the trial (minimum sample size=6 and maximum =45 (Phase I: 24 + Phase Ib: 15 + 6 for unevaluable/ineligible patients over the whole trial)).

At the time of adding schedule B, 14 participants had been treated of which 12 are evaluable for dose escalation. With the addition of 2 more doses we expect to treat 12 to 15 more patients for a total of ~29 on the phase I portion of the trial, thus we expect the trial sample size to stay within the above planned limit of 45.

Our accrual is just over 1 participant a month so the phase I portion should be completed after 2 years from start of the trial. We will need to follow the last patient for 4 months to get EFS at 4 months on the 12 patients studied at the RP2D, and expect to do the initial assessment of activity at approximately 2 1/2 years. If 6 or more of the patients studied at the RP2D are event free we will add on 15 additional patients. Based on the same accrual rate we should complete the accrual of the Phase Ib portion within approximately 12 months or and 42 months after start of the study.

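### The sample-size maximum of 45 was not re-derived after schedule B was added: its Phase I part of 24 is a simulated 95% limit for the original four doses, and section 11.2 itself now forecasts about 29

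*Combined protocol and SAP*

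**What the plan says.** - Section 11.2 builds the overall figure as "maximum =45 (Phase I: 24 + Phase Ib: 15 + 6 for unevaluable/ineligible patients over the whole trial".
- Section 4.1 calls the Phase I part a maximum: "the TEQR design will use a minimum of 6 patients and a maximum of 24 patients (median of 18) to determine the MTD". The synopsis says the same.
- Section 11.1.1 gives the source of that number. Over 1,000 simulated trials on the original four dose levels, "the median sample size was 18 with 95% confidence limits of 12 and 24". Table 11.3 has no scenario for B1 or B-1.
- On schedule B, section 11.2 reports that "14 participants had been treated of which 12 are evaluable for dose escalation". It expects 12 to 15 more to be treated, about 29 in Phase I, and concludes: "thus we expect the trial sample size to stay within the above planned limit of 45".
- Section 8.1.1 requires patients not evaluable for toxicity to be replaced.
- Section 11.1.2 adds 15 patients if 6 or more of the first 12 are event free, with no condition on total enrolment. The final rule is: "If 16 or more patients out of the 27 are event free we will determine the combination worthy of further study". No cut-off is given for any other number.

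**The concern.** A percentile of a simulation has been carried into the plan as a ceiling. The total built on it was then kept after the design behind it changed. The forecast of about 29 in Phase I already exceeds the 24 that still stands in the sum.

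Two things are at stake. One is whether 45 is a usable enrolment figure for the amended trial. The other is what happens to the primary Phase Ib decision if enrolment approaches 45 before 27 patients have been treated at the RP2D. The error rates of 0.1 and 0.1 belong to 12 + 15 patients with a cut-off of 16. The plan does not say whether 45 binds, or how a shorter stage 2 would be judged.

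**Working it through.** **1. The plan's own figures reproduce.**
- Simon design. Inputs from 11.1.2: p0 = 0.45, p1 = 0.70, n1 = 12, stop at 5 or fewer, n2 = 15, success at 16 or more. P(success) = sum over x = 6 to 12 of b(x; 12, p) × P(Bin(15, p) ≥ 16 − x). This gives 0.091 at p = 0.45 and 0.903 at p = 0.70. The design is correct.
- Phase I size. Simulating the rules of 11.1.1 under the four scenarios of Table 11.3 gives a pooled median of 18 and 95% limits of 12 and 24, as stated. Phase I exceeds 24 in 0.7–2.5% of runs, depending on the scenario, and exceeds 30 in about 0.01%. So 24 is a percentile, although with the reserve of 6 the original 45 was nearly always enough.

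**2. The amended total.**
- Forecast: 14 + 12 + 15 = 41 to 14 + 15 + 15 = 44.
- Left for patients beyond the forecast: 45 − 44 = 1 to 45 − 41 = 4, against an allowance of 6 in the sum.
- Places for schedule B if stage 2 is to have its 15: 45 − 14 − 15 = 16, including every unevaluable patient.

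**3. What the written rules can require on schedule B.** Twelve evaluable patients suffice if B1 is kept throughout. Other paths are longer: 9 at B1 followed by 12 at B-1 is 21. The longest is 12 at B1, closed at 7 DLTs, plus 12 at B-1, which is 24 and gives 14 + 24 + 15 = 53. The 24-patient path occurs in well under 1% of simulated trials.

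**4. How often more than 16 places are needed.** The documents give no DLT rates for B1 and B-1, so these are assumptions. Schedule B is taken as a two-level ladder starting at B1 with no return to schedule A. Trials that find no RP2D are excluded. Unevaluable patients are replaced in Phase I only.

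| Assumed DLT rate B1 / B-1 | None unevaluable | 1/14 | 2/14 (observed) |
|---|---|---|---|
| 0.20 / 0.10 | 3–4% | 8% | 18% |
| 0.25 / 0.10 | 6% | 13% | 25% |
| 0.30 / 0.15 | 11% | 20% | 33% |
| 0.35 / 0.20 | 15% | 26% | 41% |
| 0.40 / 0.25 | 19% | 31% | 48% |

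The observed rate is itself uncertain: the exact 95% interval for 2 of 14 is about 2–43%. Section 11.1.1 also lists 8 + 3 = 11 evaluable participants where 11.2 says 12. With 11 the rate would be 3/14.

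**5. If 45 did bind.** The formula of step 1, with n2 = n − 12:

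| n at RP2D | Power, cut-off 16 | Type I error, cut-off 16 | Smallest cut-off with type I error ≤ 0.10 | Its power |
|---|---|---|---|---|
| 27 | 0.903 | 0.091 | 16 | 0.903 |
| 26 | 0.863 | 0.064 | 16 | 0.863 |
| 25 | 0.804 | 0.043 | 15 | 0.888 |
| 24 | 0.72 | 0.027 | 15 | 0.839 |
| 23 | 0.618 | 0.015 | 14 | 0.870 |
| 22 | 0.494 | 0.008 | 14 | 0.809 |
| 21 | 0.363 | 0.004 | 13 | 0.846 |
| 20 | 0.24 | 0.002 | 13 | 0.771 |

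**The case against.** The strongest reply is that nothing fails if the plan is followed as written. The forecast totals 41 to 44, inside 45. Section 11.2 states an expectation, not a stopping rule. Section 11.1.2 adds the 15 patients unconditionally, and with 27 patients the power is 0.90. The figure could also be revised by amendment, as the dose levels were. All of this stands, and it limits the point.

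A reader might infer more than the documents support:
- *That 45 cannot hold the amended trial.* The plan's own arithmetic shows that it can. Because 12 to 15 counts treated patients, 15 treated would still give 12 evaluable at B1 with 3 unevaluable.
- *That the mislabelled 24 causes a shortfall.* It does not, since the original Phase I almost never passed 24 + 6 = 30. The pressure comes from the 14 places already used, the added dose levels and the replacements.
- *That the unevaluable rate carries into stage 2 and makes a shortfall likely.* The replacement rule in 8.1.1 concerns evaluability for toxicity. No section says that stage 2 patients are replaced for the EFS endpoint.
- *That the trial will lose power.* That requires both a hard stop at 45 and a cut-off of 16 applied to fewer than 27 patients. The documents state neither.

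What remains after the reply is a figure labelled a maximum that is not one, a sum that no longer matches the forecast beside it, and no statement of whether it binds.

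**Conclusion.** The point holds as a defect in the stated sample size, not in the Phase Ib test, whose error rates are correct. The 24 is the upper 95% simulated limit of a four-dose design that has since been changed, and 45 is not a maximum of the amended design. It fits the forecast with 1 to 4 places to spare, and the written rules can exceed it.

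Under the assumed DLT rates and the two-level ladder, more than 16 schedule B places are needed in about 3–19% of trials with no further unevaluable patients, 8–31% at 1/14 and 18–48% at 2/14 in Phase I only. These ranges rest on assumptions that the documents do not supply. They show that the margin is thin, but they do not predict what will happen.

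The loss of power is conditional. It arises only if 45 is enforced against 11.1.2 with the cut-off left at 16: 0.86 at n = 26, 0.80 at n = 25 and 0.62 at n = 23.

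**What to change.** 1. In the synopsis, 4.1 and 11.2, describe 24 as the upper 95% simulated limit of the original four-dose design.
2. In 11.2, replace 45 by a total from the sponsor's own simulation of the amended design, with a stated allowance for unevaluable patients. State that stage 2 completes its 15 patients (27 at the RP2D) regardless of that planning figure, in line with 11.1.2.
3. Only if 45 is to be a hard limit, prespecify final cut-offs for the attained number at the RP2D, keeping the 5-of-12 first stage and type I error at or below 0.10. These are 16 of 26–27, 15 of 24–25, 14 of 22–23 and 13 of 20–21, with power 0.86–0.90, 0.84–0.89, 0.81–0.87 and 0.77–0.85.

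The cost is one rerun of the simulation and some wording, with no added procedure for patients. The drawback is a less favourable stated maximum or, under step 3, a stated power below 0.90 whenever fewer than 27 are reached.
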